**Assessing the Impact of Herbal Supplement on Fatigue and Disease Activity in SLE:
Results from an 8-Week Randomized Trial**

20-01-2026

Introduction

Systemic lupus erythematosus (SLE) is a chronic auto-immune disease with a wide range of clinical manifestations and a complex pathogenesis. Despite advancements in treatments for disease activity, fatigue continues to be one of the most prominent and unresolved complaints among patients [1].

According to Jianhua Shen et al. [2], fatigue is defined as an overwhelming sense of tiredness, a lack of energy, and a feeling of exhaustion that is associated with impaired physical and/or cognitive functioning. The prevalence of fatigue in SLE may reach up to 90%, according to some studies[3]. Moreover, over 50% of patients report it as their most disabling symptom[3]. Stress, depression, pain, disease activity, and disease duration are among the most common contributors to fatigue in these patients. Fatigue significantly impacts quality of life (QoL) across all domains physical, psychological, and socio-occupational. Management recommendations for fatigue typically involve a combination of pharmacologic and nonpharmacologic approaches; however, no specific medications have been shown to be effective in treating fatigue associated with SLE[4].Hence, it is essential to evaluate and identify potential intervention areas to alleviate patients' symptom burden and enhance their overall quality of life.

Therefore, we opted for the dietary supplement EVACUR.It is a dietary supplement designed to help combat fatigue and boost the immune system. It combines natural extracts, vitamins, and selenium to support overall vitality.

The aim of our double-blind, placebo-controlled randomized trial was to evaluate the efficacy of using herbal-based treatment on patients with SLE-related fatigue .

Methods:

Study Type:

This was a randomized, double-blind clinical trial conducted in two internal medicine departments in Tunisia over a period of 3 months.

Study Population:

Patients with a diagnosis of SLE who were being followed in the participating departments.

Inclusion Criteria:

- Age > 18 years
- Confirmed diagnosis of SLE according to the 2019 ACR/EULAR classification criteria
- Presence of fatigue, defined as a FACIT-F score < 34
- Signed informed consent

Non-Inclusion Criteria:

- Pregnancy or breastfeeding
- Diseases or comorbidities that may influence fatigue:untreated hypothyroidism, psychosis common infections, and other autoimmune and inflammatory diseases
- Patients on vitamin K antagonist therapy, due to a possible interaction with Ginger and Nigella
- History of severe allergy or intolerance to EVACUR or any component of the placebo

Exclusion Criteria:

- Diagnosis of another systemic disease during the study period
- Pregnancy
- Allergy to any component of EVACUR
- Withdrawal of consent

Data Collection:

Patient data were collected from medical records, including epidemiological characteristics such as age at inclusion, gender and medical and family history. Disease-specific data included the duration of disease,

systemic manifestations, nature of treatment at inclusion. Disease activity was evaluated using clinical SLEDAI-2K score. Baseline FACIT score was collected. Biological assessments were performed such as Anti-dsDNA antibody titers, ANA and serum C3 and C4 levels.

Study protocol:

Randomization:

A two -to-one (2:1) randomization was performed in this study in which patients were randomly assigned into two groups: Group 1 (G1) which received EVACUR, and Group 2 (G2) received a placebo. Randomization was handled by an independent third party using a dedicated randomization software.

Double-Blind Design:

Neither the patients nor the investigators knew the treatment assignment. EVACUR and placebo capsules are identical in appearance.

Treatment:

EVACUR:

A phytotherapeutic compound presented in capsule form. Each bottle contains 40 capsules composed of: Nigella seed, Zinc sulfate, Echinacea, Vitamin C, Red ginseng, Ginger, Chamomile, Spirulina, Royal jelly, Ganoderma, Vitamins B1, B6, B12, Selenium(**Table1**).

Contra-indications: Allergy to any component of the supplement.

Placebo:

Capsules containing starch, packaged identically to EVACUR bottles.

Both treatments will be administered at a dose of 2 capsules per day in the morning (3 bottles per patient for the study duration).

Follow-up:

Patients attended three visits at baseline**M0**, one month**M1**, and two months**M2**. The FACIT score was assessed during each visit along with a physical examination.

Adverse Events:

Potential side effects will be recorded and evaluated throughout the study. Occurrence of any adverse event will lead to patient exclusion and trigger a pharmacovigilance investigation. All adverse events must be reported immediately to the principal investigator.

Fatigue Assessment Score:**Functional Assessment of Chronic Illness Therapy – Fatigue (FACIT-F)**

A 13-item questionnaire with responses on a Likert scale from 1 (not at all) to 5 (very much).

Total score out of 52; higher scores indicate less fatigue. Can be calculated if at least 50% of the questions are answered.

Reliability: High (Cronbach's alpha = 0.94)

Validity: Strong, with good correlation with other fatigue measurement tools

Completion time: 5–10 minutes

A validated Arabic version is available with good psychometric properties .

Evaluation Criteria:**Primary Endpoint:**

A mean Facit-F score improvement between G1 and G2 at month2 > Minimal Clinically Important Difference(MCID). The MCID in SLE is estimated at 3.4T[5].

Secondary Endpoints:

Improvement in the disease activity SLEDAI score

Good tolerance of the dietary supplement.

Statistical Analysis:

Data were analyzed using SPSS. Appropriate statistical tests will be applied, including Student's t-test or the Wilcoxon test. Randomization will be conducted using dedicated software.

Ethical considerations

This study was conducted according to the Declaration of Helsinki and approved as well by the RABTA hospital's ethics committee under the number of CERB33/2023. Informed consent was given by each patient before starting the study. Each patient will be assigned an inclusion number used for randomization and data entry, ensuring patient confidentiality.

Statements & declarations:

- **Funding:** Wellnet Pharmaceutical Factory ® provided the dietary supplement and the placebo free of charge. No additional funding was required
- **Conflict of Interest:** Wellnet Pharmaceutical Factory® had no role in the study design, data collection, analysis, interpretation, or decision to submit the manuscript for publication.

-Informed consent

Informed consent was obtained from all individual participants included in the study after reading and agreeing with the details of this trial.

- **Availability of data and material :** data are available on request from the authors

- **Ethics approval :** Patients' anonymity was maintained throughout the study. The study was approved by the ethics committee of the hospital under the number CERB 33/2023.

Table 1. Ingredients and Dosage of EVACUR Formulation per Capsule

Ingredient	Latin/INCI Name	Form/Quality	Quantity per capsule
Black seed	Nigella sativa	Dry extract	80 mg
Echinacea	Echinacea spp.	Dry extract	40 mg
Ginger	Zingiber officinale	Dry extract	30 mg
Chamomile	Matricaria chamomilla	Dry extract	10 mg
Red ginseng	Panax ginseng	Dry extract	10 mg
Reishi mushroom	Ganoderma lucidum	Dry extract	10 mg
Spirulina	Spirulina spp.	Dry extract	60 mg
Royal jelly	Royal jelly	Lyophilized	20 mg
Vitamin C	Ascorbic acid	—	30 mg
Zinc	Zinc sulfate	—	2.5 mg
Vitamin B1	Thiamine	—	3 mg
Vitamin B6	Pyridoxine	Marine source	4 mg
Vitamin B12	Cobalamin	—	10 µg
Selenium	Selenium yeast	—	40 µg

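### The allergy rule at entry is narrower than the contra-indication and the exclusion criterion, so a patient with a known contra-indicated allergy can be randomised

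*Protocol*

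**What the plan says.** Three places in the Methods of the protocol deal with allergy.

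- Non-Inclusion Criteria: "History of severe allergy or intolerance to EVACUR or any component of the placebo".
- Exclusion Criteria: "Allergy to any component of EVACUR".
- Treatment, under EVACUR: "Contra-indications: Allergy to any component of the supplement".

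The Exclusion Criteria form a list separate from the Non-Inclusion Criteria. They include "Diagnosis of another systemic disease during the study period" as well as withdrawal of consent, so the list describes removal after enrolment rather than a second screen.

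On allocation the protocol states "A two -to-one (2:1) randomization was performed in this study", with the larger group on EVACUR. On blinding it states "Neither the patients nor the investigators knew the treatment assignment". The placebo is described as "Capsules containing starch, packaged identically to EVACUR bottles". Under Adverse Events there is a separate removal rule: "Occurrence of any adverse event will lead to patient exclusion and trigger a pharmacovigilance investigation".

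**The concern.** The rule that decides who may be randomised is the narrowest of the three. A patient with a known mild allergy to, say, ginger or chamomile is not stopped by any listed entry criterion, although the same protocol treats that allergy both as a contra-indication and as a ground for removal.

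Two things are at stake. The first is safety: such a patient may be given a product that the protocol says is contra-indicated for them, with neither patient nor investigator knowing which capsule was received. The second is conduct: a characteristic that one screening question would reveal becomes a reason to remove the patient after randomisation. The two participating departments, each following the written lists, could also decide differently about the same patient.

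**Working it through.** The protocol gives no figure on this point, so there is none to reproduce. The check is a comparison of wording, followed by a short calculation of where removals would fall.

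**Step 1: scope of each rule.**

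| Rule | Severity | What it names | When it acts |
|---|---|---|---|
| Non-inclusion | Limited to severe (the adjective may or may not also govern intolerance) | EVACUR as a product; components of the placebo | Before randomisation |
| Exclusion | No limit | Any component of EVACUR | After enrolment; no trigger stated |
| Contra-indication | No limit | Any component of the supplement | Not tied to a visit or to eligibility |

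The second and third rows match. Only the first differs: it adds a severity limit, and it attaches the reference to components to the placebo and not to EVACUR.

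**Step 2: follow one patient through.** Take a known non-severe allergy to a Table 1 ingredient.

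- Entry: not severe, so not barred by the allergy criterion. No other listed criterion applies.
- Treatment: contra-indicated.
- After enrolment: the exclusion criterion is met as worded, since it does not require the allergy to be new.

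If the exclusion criterion was meant only for allergy that shows itself on treatment, the third step falls away. The conflict between entry and contra-indication remains.

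**Step 3: chance of exposure.** With 2:1 allocation, P(EVACUR) = 2/(2 + 1) = 66.7% for each such patient. This needs no assumed prevalence.

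**Step 4: how removals would divide between arms.** Let k = 2 be the allocation ratio. Let RR be the removal rate on EVACUR divided by that on placebo, among patients with a component allergy. Then

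share of removals from EVACUR = k × RR / (k × RR + 1).

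RR is not in the protocol, so a range is shown:

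| RR | Share from EVACUR |
|---|---|
| 1 | 2/3 = 66.7% |
| 2 | 4/5 = 80.0% |
| 3 | 6/7 = 85.7% |
| 5 | 10/11 = 90.9% |
| 20 | 40/41 = 97.6% |

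A 90% share needs RR = (0.90/0.10)/2 = 4.5. A 95% share needs RR = (0.95/0.05)/2 = 9.5.

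A known allergy found from the history is acted on without knowledge of the arm, so RR = 1 is the value to expect. The split is then simply the allocation, and each arm loses the same expected fraction of its patients.

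**The case against.** Several arguments can be made for the plan as written.

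*A wider rule on study beside a narrower rule at entry is not in itself a contradiction.* This is true in general, and pregnancy also appears in both lists. For pregnancy, however, the entry rule is at least as wide as the exclusion rule. For allergy it is narrower, and the gap is a history that can be asked about before randomisation.

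*Allergy to EVACUR naturally includes allergy to what it contains.* This is a fair reading, and the component gap should not be pressed hard. The severity limit remains on any reading.

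*The contra-indication is protocol text, so clinicians would apply it.* They may well do so. But it stands in the product description, and no eligibility criterion refers to it. Elsewhere the entry list does work at ingredient level: the vitamin K antagonist criterion names Ginger and Nigella.

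*Much of the document is in the past tense, so a new screening rule may come too late.* This stands, and it changes the remedy rather than the finding.

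A reader might go further and infer that the removals would fall almost entirely on the EVACUR arm and so flatter both the FACIT-F comparison and the tolerance endpoint. The document does not support that.

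- For a known allergy, the exclusion applies whichever capsule was received and under blinding, so the rates should be equal and the expected difference between arms is not shifted.
- Near one-sided loss needs removal triggered by reactions to an EVACUR ingredient, which is plausible against a starch placebo. A patient who reacts is in any case removed under the rule on adverse events, which applies in both arms. That loss belongs mainly to that rule, and harmonising the allergy wording would not cure it.
- Nothing says that excluded patients leave the tolerance count. Whether their FACIT-F data are dropped is also not stated, and may be settled in a statistical analysis plan that is not at hand.

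**Conclusion.** The point holds as a conflict between one rule and two others. The entry criterion is narrower than the contra-indication and the exclusion criterion, which agree with each other. As written, a patient with a known non-severe component allergy can be randomised, has a 2-in-3 chance of receiving a product listed as contra-indicated, and then qualifies for removal.

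This rests on reading the criteria literally and on taking the Exclusion Criteria to act after enrolment, which their contents support. No differential bias between arms is claimed. The number of patients affected and any effect on the FACIT-F result cannot be calculated, because sample size, allergy prevalence and reaction rates are not given. The weight of the point lies in safety and consistency, and the correction is cheap enough that it should be made.

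**What to change.** Reconcile the three statements so that the eligibility list, the contra-indication and the exclusion criterion agree on severity and on which components are covered, and apply the agreed rule before randomisation. Which wording to adopt is for the investigators and the ethics committee. It would also help to state what the post-enrolment criterion is for: an allergy found from history, a reaction on treatment, or both.

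If enrolment is already complete, report which allergy rule was actually applied at screening in each department, and give allergy-related removals by arm and by reason.

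The cost is a wording amendment and, depending on the rule chosen, possibly a few more screen failures. If the trial is finished, it is a sentence and a small table in the report.

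### Any adverse event excludes a randomised patient, with no threshold and no provision for FACIT-F follow-up to month 2, so the primary comparison may not be as randomised

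*Protocol*

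**What the plan says.** The operative sentence is in the protocol's Adverse Events section: "Occurrence of any adverse event will lead to patient exclusion and trigger a pharmacovigilance investigation". The same section says "Potential side effects will be recorded and evaluated throughout the study" and requires immediate reporting to the principal investigator. It gives no grade, seriousness or relatedness limit.

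The protocol separates Non-Inclusion Criteria, which apply at entry, from Exclusion Criteria, which apply on study. The second list includes "Diagnosis of another systemic disease during the study period" and "Withdrawal of consent", along with pregnancy and allergy. It does not list adverse events in general.

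Under Follow-up, visits are at M0, M1 and M2, and "The FACIT score was assessed during each visit along with a physical examination". The Primary Endpoint is "A mean Facit-F score improvement between G1 and G2 at month2", set against an MCID of 3.4 points. SLEDAI improvement and tolerance are the Secondary Endpoints. No section says whether an excluded patient attends the remaining visits.

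**The concern.** The rule acts after randomisation and is triggered by something treatment can affect. The comparison is a 14-ingredient supplement against starch, so event rates could differ by arm. Blinding does not protect against this, because the imbalance would come from the capsules and not from knowledge of allocation.

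The trigger may also be related to fatigue. Infection is the clearest example. The Non-Inclusion Criteria name "Diseases or comorbidities that may influence fatigue:untreated hypothyroidism, psychosis common infections, and other autoimmune and inflammatory diseases", and the Introduction describes EVACUR as "a dietary supplement designed to help combat fatigue and boost the immune system". An infection during the study would ordinarily count as an adverse event. On the protocol's own premises, then, one plausible kind of event could bear on both outcome and treatment.

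If such patients leave before M2, the FACIT-F comparison is made among those who stayed free of events, which is not the randomised comparison. The SLEDAI comparison may be affected too, although its post-baseline timing is not stated. For tolerance, the first event is captured, but observation of later events in the same patient may stop.

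**Working it through.** **What the text implies.** Three readings of *exclusion* are possible.

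- Stopping capsules only: M2 can still be measured, and the shift is 0.
- Leaving study visits: M2 is lost when the event comes before that visit.
- Leaving the analysis: M2 is unused even if it was measured.

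The Exclusion Criteria include withdrawal of consent, so the word is not confined there to stopping capsules. The second or third reading is the more natural one, but the text does not settle it.

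**Inputs.** From the protocol: 2:1 allocation and an MCID of 3.4. It states no event rate, standard deviation, sample size or dropout, so there is no figure to reproduce. Everything else is assumed, for illustration only:

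- p, the proportion of an arm with an adverse event: 10% to 30%
- d, how many points worse affected patients score at M2: 2 to 8
- f, the share of affected patients whose M2 is lost: 1, or 0.5 if, for example, half of the events are first reported at the M2 visit

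**Formula.** Let m be the mean M2 score of event-free patients in an arm. The mean of the whole arm is m - d·p. Among patients retained, the share with an event is p(1-f)/(1-pf), so the retained mean is m - d·p(1-f)/(1-pf). The shift in that arm is the difference:

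shift = d·p·f·(1-p)/(1-pf), which is d·p when f = 1.

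The shift in G1-G2 is the G1 shift minus the G2 shift. Positive values favour EVACUR.

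| Rates G1/G2 | d (G1/G2) | f | Shift in G1-G2 | Share of 3.4 |
|---|---|---|---|---|
| 10%/10% | same | 1 | 0 | 0% |
| 20%/10% | 4/4 | 1 | 4 × 0.10 = +0.4 | 12% |
| 10%/20% | 4/4 | 1 | -0.4 | 12% |
| 30%/10% | 8/8 | 1 | 8 × 0.20 = +1.6 | 47% |
| 10%/30% | 8/8 | 1 | -1.6 | 47% |
| 20%/10% | 4/4 | 0.5 | 4 × (0.0889 - 0.0474) = +0.17 | 5% |
| 30%/10% | 8/8 | 0.5 | 8 × (0.1235 - 0.0474) = +0.61 | 18% |
| 30%/10% | 8/2 | 1 | 2.4 - 0.2 = +2.2 | 65% |
| 30%/10% | 8/2 | 0.5 | 0.988 - 0.095 = +0.89 | 26% |

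Mirror-image inputs give the same sizes with a negative sign.

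**Precision.** Under 2:1 allocation the share of patients missing M2 is f(2p₁+p₂)/3. With equal SDs, the standard error is multiplied by √{[1/(2(1-f·p₁)) + 1/(1-f·p₂)]/1.5}.

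| Rates G1/G2 | f | Missing M2 | SE ratio |
|---|---|---|---|
| 10%/10% | 1 | 10.0% | 1.054 |
| 30%/10% | 1 | 23.3% | 1.103 |
| 10%/30% | 1 | 16.7% | 1.150 |
| 30%/30% | 1 | 30.0% | 1.195 |
| 10%/10% | 0.5 | 5.0% | 1.026 |
| 30%/30% | 0.5 | 15.0% | 1.085 |

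**The case against.** The strongest reply is that the harm hangs on one undefined word. Adverse events are not in the Exclusion Criteria list, so that list does not settle what exclusion means after one. If it means stopping capsules, nothing is lost. This stands as a limit on the size of the problem. It does not clear the protocol, because sites need to know whether to collect the M2 score and the text does not tell them.

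The paragraph also opens with side effects and ends the disputed sentence with a pharmacovigilance investigation, so only suspected product reactions may have been meant. That is possible, but the sentence says any adverse event. The investigation is genuine safety follow-up of the event; what is missing is continued FACIT-F and visit follow-up.

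The infection example is suggestive only. The immune claim is a product description, and the protocol nowhere says EVACUR changes infection rates. If it did reduce infections, placebo would lose more low scorers and the shift would be negative, against EVACUR. More events on active capsules than on starch would, with the same d in both arms, push the other way. The direction is therefore open.

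The 47% figure needs a threefold rate difference, a d more than twice the MCID, and loss of every affected M2 score. The moderate case is 12%, or 5% if half are lost.

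Finally, the title and much of the text suggest follow-up is finished, and an analysis plan that is not shown may define the analysis set. Such a plan can decide who is analysed and how gaps are handled, but it cannot recover scores that were not collected.

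**Conclusion.** The concern holds. As written, the rule can remove randomised patients before the primary measurement, for a reason that may be tied to arm and outcome, and nothing in the protocol keeps them in FACIT-F assessment. The missing threshold is plain from the text. The loss of M2 scores depends on reading exclusion as removal from the study, which the Exclusion Criteria support but do not prove.

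Neither the size nor the direction of any shift can be known from the protocol. On the assumed inputs it is 0 with equal rates and equal d, 0.4 points in a moderate case, and at most 1.6 points with the same d in both arms or 2.2 with different d, in either direction. With few events it would be small. The point should be fixed, because the rule bears on the primary comparison and the remedy is cheap.

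**What to change.** **If follow-up is not complete,** replace the sentence with wording such as:

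> Any adverse event is recorded, reported immediately and triggers a pharmacovigilance investigation. Capsules are stopped when the investigator judges it clinically necessary (always for suspected allergy). Whether or not capsules are stopped, the patient stays in follow-up to M2 and is analysed in the randomised group unless consent is withdrawn.

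This costs three sentences and uses the M1 and M2 visits already planned. The downside is a few visits by patients off capsules and a possibly diluted effect. Stopping capsules for safety is retained.

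**If follow-up is complete,** rewording changes nothing and lost M2 scores cannot be recovered. Report exclusions by arm and reason, and state what exclusion meant in practice. Analyse all randomised patients using the available M1 and M2 data, with sensitivity analyses for missing M2 values, and count adverse events in all treated patients. The cost is one table and the extra analyses.

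### The primary endpoint is a cut-off on the observed FACIT-F difference (> 3.4), but the named tests by default test for no difference, and the two can disagree

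*Protocol*

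**What the plan says.** Under Evaluation Criteria, the Protocol gives the primary endpoint as "A mean Facit-F score improvement between G1 and G2 at month2 > Minimal Clinically Important Difference(MCID"). The threshold follows: "The MCID in SLE is estimated at 3.4T[5"] (the T looks like a stray character). The Statistical Analysis section says only "Appropriate statistical tests will be applied, including Student's t-test or the Wilcoxon test". It states no null value and no rule that links the test result to the 3.4.

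Three other statements bear on the point:

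- Allocation (Randomization): "A two -to-one (2:1) randomization was performed in this study".
- Data available (Data Collection and Follow-up): "Baseline FACIT score was collected" and "The FACIT score was assessed during each visit along with a physical examination", with visits at M0, M1 and M2.
- Status: the title contains "Results from an 8-Week Randomized Trial" and the analysis section begins "Data were analyzed using SPSS", so the trial may already have been analysed.

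**The concern.** The endpoint sentence names an instrument, a contrast and a time point, but it also builds a numerical result into the endpoint: the mean difference must exceed 3.4. The tests named a few lines later answer a different question by default, namely whether the difference is zero. The Wilcoxon test does not address a difference in means at all.

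The role of 3.4 is therefore unsettled. It could be the whole success rule, a condition on top of significance, or an aid to interpretation. The first is the literal wording. At stake is the verdict on the trial: a non-significant difference just above 3.4 could be reported as success, and a clearly significant one just below it as failure.

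**Working it through.** **Inputs.** From the Protocol: threshold 3.4, allocation 2:1, endpoint at month 2. Not in the Protocol, so assumed for illustration: SD 6 to 12, total N of 60 or 180, two-sided 5%. The Protocol gives no sample size, power or SD, so it has no figure of its own to reproduce.

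**Standard error.** With 2N/3 and N/3 patients per group, SE = SD × √(1/(2N/3) + 1/(N/3)) = SD × √(4.5/N).

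**Literal rule.** By normal approximation, P(success) = P(Z > (3.4 − d)/SE) for a true difference d. At d = 3.4 this is P(Z > 0) = 50%, whatever N and SD. At d = 0 it is P(Z > 3.4/SE). The zero test needs an estimate above about 1.96 × SE.

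| N | SD | SE | Smallest significant difference (1.96 × SE) | False success of the literal rule at d = 0 |
|---|---|---|---|---|
| 60 | 6 | 1.643 | 3.22 | 1.9% |
| 60 | 8 | 2.191 | 4.29 | 6.0% |
| 60 | 10 | 2.739 | 5.37 | 10.7% |
| 60 | 12 | 3.286 | 6.44 | 15.0% |
| 180 | 6 | 0.949 | 1.86 | below 0.1% |
| 180 | 8 | 1.265 | 2.48 | 0.4% |
| 180 | 10 | 1.581 | 3.10 | 1.6% |
| 180 | 12 | 1.897 | 3.72 | 3.7% |

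The comparator is 2.5%, the chance that a two-sided 5% test favours G1 when there is no effect.

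**Where the rules cross.** Setting 1.96 × SE = 3.4 gives N = 4.5 × (1.96 × SD/3.4)², which is about 54 (SD 6), 96 (SD 8), 150 (SD 10) and 215 (SD 12). Below that N the literal rule is looser than the zero test; above it, stricter.

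**Disagreement in both directions (two-sample t-test, N − 2 degrees of freedom).**

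- Observed 3.6 at N = 60, which meets the endpoint: SD 8 gives t = 3.6/2.191 = 1.64, p = 0.11, 95% CI −0.8 to 8.0. SD 10 gives p = 0.19 and SD 12 gives p = 0.28. With SD 6, p = 0.03 and the two rules agree.
- Observed 3.2 at N = 180, which fails the endpoint: SD 8 gives t = 3.2/1.265 = 2.53, p = 0.012, 95% CI 0.7 to 5.7.

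**The case against.** The strongest reply is that this is detail for an SAP, which is not at hand. Null value, significance level and the way an estimate and a p-value combine are often settled there. The list of tests is open-ended, and a t-test can be run against 3.4, so nothing in the text is strictly impossible. On an ordinary reading, the sponsor means to compare mean FACIT-F at M2 and call the result meaningful if it exceeds the MCID. Part of this stands: the Protocol contains no wrong number here, and the intention may be sound. But the Protocol itself placed the threshold inside the primary endpoint. An SAP that tested against zero alone would depart from that wording, and one that kept 3.4 would have to say how it operates.

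A second reply is that the size depends on the assumed SD. This stands too. At SD 6 the literal rule is already slightly stricter than the zero test at N = 60. A fairly low SD is plausible, since entry requires a FACIT-F score below 34 and baseline adjustment would reduce the residual spread.

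A reader might infer three stronger claims that the document does not support:

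- **That false positives are inflated in this trial.** N and SD are unstated, and above the crossover N the literal rule is the stricter one.
- **That the lower confidence limit must exceed 3.4.** Nothing in the text mentions a confidence limit, so this reading is remote.
- **That 3.4 is the wrong kind of MCID for a group contrast.** Its source is not at hand, so this cannot be judged.

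**Conclusion.** The point holds as a badly fixed decision threshold and should be fixed. As written, the primary endpoint is met or missed on the point estimate, with no controlled error rate, and it need not agree with the tests named to analyse it. That conclusion needs no assumption about N or SD. The size does: across the assumed range the literal rule runs from far stricter than the zero test to six times its 2.5% false-success rate (15.0/2.5 = 6). Which of these applies here cannot be told from the document, so the finding is about an unclear and uncontrolled success rule, not about demonstrated harm.

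**What to change.** Define the primary endpoint as the between-group difference (G1 versus G2) in FACIT-F at M2, adjusted for the M0 score. Test it against zero at two-sided 5%, report it with a 95% confidence interval, and use 3.4 only to interpret the estimate and interval. If the sponsor wants exceeding the MCID to be necessary for success, say so and require it together with significance against zero, not in place of it. If an SAP already settles the matter, align the Protocol wording with it.

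No new data are needed, because FACIT is recorded at M0 and M2. There are two costs. An estimate above 3.4 no longer suffices alone. At larger N, a significant difference below 3.4 counts statistically, with its relevance left to interpretation; at SD 8 and N = 180 that is roughly 2.5 to 3.4.

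If the data are already unblinded, as the title and the past tense of the analysis section suggest, the restatement must be disclosed as post hoc and the result under the Protocol's present wording reported beside it. In that case the gain is mainly clear disclosure.

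### The primary endpoint is a between-arm difference in mean FACIT-F, but the protocol leaves open a Wilcoxon test, which neither tests nor estimates that difference

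*Protocol*

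**What the plan says.** The Protocol, under Evaluation Criteria, gives the primary endpoint as "A mean Facit-F score improvement between G1 and G2 at month2 > Minimal Clinically Important Difference(MCID" and puts the MCID at 3.4 points. The summary measure is therefore a mean, the contrast is between arms, and the unit is FACIT-F points.

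The Statistical Analysis section contains one sentence on tests: "Appropriate statistical tests will be applied, including Student's t-test or the Wilcoxon test". It ties neither test to an endpoint, gives no rule for choosing, and does not say which Wilcoxon test is meant. The sentence before it reads "Data were analyzed using SPSS", so the section is partly in the past tense and partly in the future.

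Three design features bear on the remedy. Allocation is unequal ("A two -to-one (2:1) randomization was performed in this study"). Entry is restricted on the outcome scale itself ("Presence of fatigue, defined as a FACIT-F score < 34"). A baseline value exists for every patient, because "The FACIT score was assessed during each visit along with a physical examination" and the first visit is baseline.

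**The concern.** A t-test asks whether two means differ, and it comes with an estimate and confidence interval in points that can be read against 3.4. A rank-sum test asks whether a patient drawn from one arm tends to score higher than a patient drawn from the other. The two questions coincide when the arms differ only by a constant shift. They separate when the treatment changes the shape of the distribution, for example when a minority responds strongly.

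With the choice left open, the conclusion on efficacy may rest on a test of something other than the stated endpoint, and the test may be chosen after the data have been seen.

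**Working it through.** **Inputs.** From the protocol: a mean endpoint, a 3.4-point threshold, 2:1 allocation, a score out of 52, entry below 34, and visits at baseline and month 2. The protocol states no sample size, SD, alpha or correlation, so there is no planned figure to reproduce. Assumed here: arms of 40:20, 60:30 or 100:50, two-sided 5%, and SD of change 8 unless stated. Steps 1, 2 and 4 use 10,000 simulated trials per setting and step 3 uses 20,000. The tests compared are the two-sample Student's t-test and the two-sample rank-sum test.

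**1. Plain shift of 3.4 points, normal scores.** The standard error at 60:30 is 8 × √(1/60 + 1/30) = 8 × 0.2236 = 1.79, and 3.4/1.79 = 1.90, which gives t-test power of about 47%. Simulated power:

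| Arms | t-test | rank-sum | disagree on significance |
|---|---|---|---|
| 40:20 | 33.7% | 31.8% | 6.4% |
| 60:30 | 46.5% | 44.5% | 6.9% |
| 100:50 | 68.5% | 66.4% | 6.4% |

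In this ordinary case the choice hardly matters.

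**2. Equal means, different shapes.** One arm's change is exponential with mean 8, less 6 (mean 2, SD 8). The other's is normal with mean 2, SD 8. The mean difference is 0, but the chance that a patient in the skewed arm scores higher is 0.46, not 0.50.

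| Arms | t-test rejects | rank-sum rejects |
|---|---|---|
| 40:20 | 5.5% | 8.9% |
| 60:30 | 5.6% | 10.3% |
| 100:50 | 5.1% | 13.1% |

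The rank-sum rate grows with sample size because that test is detecting something real that is not the stated endpoint. Here the error runs against the skewed arm; with the skew reversed it would run in that arm's favour.

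**3. Minority response.** Suppose 20% of EVACUR patients gain 18 points and the rest gain nothing, with SD 8 around that. The mean difference is 0.20 × 18 = 3.6. Power for t-test versus rank-sum is 34% versus 27% at 60:30 and 55% versus 43% at 100:50, gaps of about 7 and 13 percentage points.

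**4. Picking the smaller p-value.** With normal scores and no effect (SD 8 or 10), at least one of the two tests is significant in 5.6-6.4% of trials, against 4.7-5.4% for the t-test alone.

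**5. What baseline adjustment gains.** Assume that, before selection, FACIT-F has mean 30, SD 10 and baseline-to-month-2 correlation 0.7. For entry below 34, z = (34 − 30)/10 = 0.4 and λ = φ(z)/Φ(z) = 0.3683/0.6554 = 0.562. The baseline variance among those enrolled is 100 × (1 − 0.4 × 0.562 − 0.562²) = 45.9. The residual variance is 100 × (1 − 0.7²) = 51.

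- Month-2 score alone: 51 + 0.7² × 45.9 = 73.5, SD 8.57.
- Change score: 51 + 0.3² × 45.9 = 55.1, SD 7.43.
- Baseline-adjusted: 51, SD 7.14.

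Multiplying by 0.2236 gives standard errors of 1.92, 1.66 and 1.60. For a 3.4-point effect at 60:30, power is about 42%, 53% and 56%.

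**The case against.** The strongest reply is that choice of test, estimator and sensitivity analyses usually belongs in a statistical analysis plan, which may exist and settle this. The sentence on tests is generic and not exhaustive. It speaks of appropriate tests, and the Wilcoxon test may have been meant for the SLEDAI score. This stands in part: applying the sentence to the primary endpoint is an inference from its being the only analysis text. What remains is that the protocol itself sets a mean-based criterion and writes an open alternative that includes a test not aimed at means. A later plan could resolve that only by ruling out one of the options for this endpoint.

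A reader might infer four stronger things, and the protocol supports none of them.

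- That Wilcoxon means the paired signed-rank test within each arm. The name also covers the two-sample test, and the endpoint is stated as G1 against G2. A paired t-test would have the same flaw, so this is not a fault of the rank test.
- That the choice of test moves the reported effect across 3.4. The protocol fixes the effect as a mean and mentions no median or Hodges-Lehmann shift. A rank p-value leaves the mean where it is; only significance can change.
- That the loss of power is large in general. The gap in step 3 needs a strong response confined to a minority, which nothing in the protocol suggests. A larger gap appears if an unequal-variance t-test is substituted, but the protocol names Student's.
- That a favourable test has already been picked. Mixed tenses do not show this.

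**Conclusion.** The point holds as a mismatch between endpoint and analysis, of modest size. Under a plain shift the two tests differ by about 2 percentage points of power, and free choice between them costs about one percentage point of type I error. The mismatch becomes material only if the arms differ in shape: a nominal 5% rank-sum test then rejected in 9-13% of trials with no difference in means. All of these figures rest on assumed arm sizes, SDs and shapes, because the protocol gives none.

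It is still worth correcting, because the open alternative can be replaced at almost no cost by an analysis that estimates the stated quantity and, under the assumptions of step 5, is also more precise than an unadjusted t-test.

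**What to change.** In Statistical Analysis, name one primary analysis: the between-arm difference in mean month-2 FACIT-F, adjusted for baseline FACIT-F by ANCOVA, reported in points with a 95% CI and read against 3.4. With baseline in the model, analysing the month-2 score or the improvement gives the same treatment effect, so the endpoint is unchanged. State also whether the estimate or the lower confidence limit is to be set against 3.4, since neither named test addresses that threshold in its default form.

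Keep a rank test only as a labelled sensitivity analysis, described as the two-sample rank-sum (Mann-Whitney) test. If the data have already been analysed, report the choice as made afterwards and show both analyses.

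The cost is a few sentences and no new data, since baseline FACIT-F is already collected. The one real loss is that with heavy-tailed scores a rank test can be the more powerful, and that advantage is given up for the primary analysis.
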